Protocol & Statistical Analysis Plan for:
Pragmatic Trial of COVID Vaccine Text Outreach Interventions

University of Pennsylvania

[name]

NCT#04834726

v. 11-16-2021

Approved: 11-19-2021

Pragmatic Trial of COVID Vaccine Text Outreach Interventions

Brief Description

This project aims to evaluate different approaches to increase COVID-19 vaccine uptake among at-risk patients at Penn Medicine in an equitable and systematic manner through a centralized outreach program. We will evaluate different text-based scheduling and messaging approaches informed by behavioral science to increase uptake among eligible patients, including the use of clinician endorsement, opt-out framing, and scarcity.

Abstract

COVID-19 is a significant cause of global morbidity and mortality. The COVID-19 vaccine can effectively reduce significant morbidity and eliminate mortality in vaccinated populations, but the pandemic has exacerbated existing racial and socioeconomic disparities in access to and uptake of the COVID-19 vaccine. In this project, we will evaluate different ways to reach out to at-risk patients to encourage them to participate in vaccination, comparing different scheduling workflows and messaging approaches informed by behavioral science with the goal of increasing COVID-19 vaccine uptake.

Data Management

Information about study subjects will be kept confidential and managed according to the requirements of the Health Insurance Portability and Accountability Act of 1996 (HIPAA). Source documents are maintained in PennChart. No source documents will be printed or maintained in paper form at the study site. Data from PennChart will be recorded in Penn Medicine's REDCap system. The investigator and study team will have access to PHI within PennChart and REDCap. We will label all PHI within REDCap as identifiable information so that de-identified exports are possible. All reports that include identifiable information will be stored on the Innovation Center secure drive, maintained behind the UPHS firewall. Direct identifiers will be maintained on RedCap until manuscript publication in case additional chart review is needed for confirmation of results. Once data analysis and manuscripts have been published, direct identifiers will be deleted from RedCap and the de-identified database will be stored on the Innovation Center secure drive.

Objectives

We will evaluate a centralized approach to increasing COVID through direct outreach to eligible patients via text messaging. This pragmatic randomized controlled trial has the following aims:

Aim 1: To conduct systematic large scale text message outreach for vaccine delivery among a defined group of Penn Medicine in a way that advances equity.

Aim 2: To offer different scheduling workflows through text messaging that might increase uptake and reduce disparities.

Aim 3: To compare the equity and efficiency of different messages informed by behavioral science, including PCP endorsement, opt-out framing, and scarcity.

Primary outcome variable(s)

The primary outcome will be the percentage of patients who complete the first dose of the COVID vaccine within 1 month of initial outreach.

Secondary outcome variable(s)

Secondary outcomes will be the completion of the first dose within 2 months, and completion of the vaccination process within 2 months of initial outreach. We will also examine the percentage of patients that are scheduled, text message responses (YES, INFO, NOT NOW, DONE), and number of phone calls made by the access center. We will compare response rates by age, race/ethnicity, sex, insurance type, and income (by zip code).

Background

The national roll-out of the COVID-19 vaccine has already revealed reduced uptake among Black patients due to barriers in the technical and logistical burden of vaccination, and overall hesitancy about receiving the vaccine. Those barriers are not distributed uniformly. Penn Medicine has played an integral role in delivering the COVID-19 vaccine to our community, but it will be challenging to ensure our approach does not exacerbate existing racial and socioeconomic disparities in the pandemic and, instead, helps overcome them.

The COVID vaccine workgroup at Penn Medicine (including the Office of CMIO, CPUP, PMMG, Access Center, Marketing, and CHCI) has identified approximately 19,000 patients with a cell phone number who are not enrolled in MyPennMedicine (MPM) and do not have an email address in the EHR and approximately 95,000 patients who have been sent an MPM message or email and have not yet scheduled an appointment. The team has already developed and implemented a protocol to send text messages (using the Way to Health platform) to offer the vaccine and help schedule through collaboration with the Access Center. Through this program, we propose to prospectively randomize scheduling workflow and messaging to identify the most effective and equitable approaches to increasing vaccine uptake. What we propose will simultaneously [1] identify the interventions with the highest response rate that can inform Penn Medicine efforts locally and [2] conduct a pragmatic trial with a rigorous analysis plan that we can broadly apply to other contexts and share with other health systems.

Study Design

Design

This is a pragmatic randomized controlled trial with a factorial design. 20,500 patients will be included and randomized to 3 study arms related to scheduling workflow in a 1:20:20 ratio to include 500 patients in the usual care arm (phone call only) and 10,000 patients in each text messaging arm as follows: 1) Phone Call (usual care), 2) Opt-In (call back), 3) Opt-in (in-bound). Among the 20,000 patients receiving text messaging (Arms 2&3), patients will be additionally randomized in a factorial design to four different types of messaging content informed by principles of behavioral science in a 1:1:1:1 ratio (5,000 in each arm): A) Standard Messaging, B) Clinician Endorsement, C) Scarcity, and D) Opt-Out Framing.

Study duration

We anticipate 2 weeks to set up the text messaging platform, and to identify and randomize eligible patients. Phone calls and text messaging will begin at the same time, and initial outreach and all follow-up messaging will be completed within 14 days from initial outreach.

Resources necessary for human research protection

[name] is the PI of this study. He is an assistant professor of medicine at the Perelman School of Medicine, University of Pennsylvania and Associate Chief Innovation Officer at Penn Medicine. All members of the research team have completed CITI human subjects research training. Standard Operating Procedure documents for the project will be accessible to all members of the research team, which will keep research staff informed about the protocol and their related duties. There are adequate facilities to conduct the research.

Characteristics of the Study Population

Target population

This program will take place across patients seen at Penn Medicine practices who reside in the city of Philadelphia.

Subjects enrolled by Penn Researchers

20,500

Subjects enrolled by Collaborating Researchers

0

Subject Recruitment

20,500 patients will be identified through automated data extraction from the electronic health record (EHR). All eligible patients will receive vaccine outreach via phone call or text message. In order to minimize the outgoing phone call burden on the access center, we will randomize 500 patients in the phone call arm (Arm 1). The remaining 20,000 patients will be randomized to receive text message based outreach.

Accrual

We will conduct the study in close partnership and with approval from the COVID vaccine workgroup for messaging and outreach methods. As a pragmatic trial, we are randomly selecting 20,500 eligible patients followed by Penn Medicine per the current city of Philadelphia eligibility guidelines for vaccination.

Key inclusion criteria:

Patients aged 18+ who reside in Philadelphia who have had at least 1 visit in the past 5 years, or a future scheduled visit within the next 3 months, with a Penn Medicine primary care provider (PCP) on file.

Key exclusion criteria:

Patients will be excluded if they have completed any dose of the vaccine at Penn Medicine, are currently scheduled, have externally documented vaccination records, or have previously received text-message based vaccine outreach.

Procedures

We request a waiver of informed consent as this is low-risk, supported by and embedded in clinical operations, and we could not practicably obtain consent. Through automated data extraction, we will identify eligible patients, along with the name of their primary care provider or the last clinician that saw them in a visit. All patients will receive outreach about scheduling an appointment to receive the COVID-19 vaccine.

Randomization:

20,000 patients will be randomized to 3 study arms related to scheduling workflow in a 1:20:20 ratio (500 usual care, 10,000 in intervention arms) to receive: 1) Phone Call (usual care), 2) Opt-In (call back), 3) Opt-in (in-bound).

- *Arm 1: Phone Call (usual care):* 500 patients will be randomized to Arm 1, Phone Call (usual care) and will receive a phone call to schedule their appointment from an Access Center representative. Access Center representatives will make up to 3 attempts to schedule an appointment with the patient. Patients randomized to this arm will not receive any text messaging.

The remaining 20,000 patients will be randomized to study arms that will receive one of 2 scheduling workflows in a 1:1 ratio (10,000 in each arm):

- *Arm 2: Opt-In (call back):* Messaging will include a prompt to agree to scheduling: "If you would like us to call you to schedule your appointment please reply, YES." The access center will call these patients back to schedule, calling up to 3 times.
- *Arm 3: Opt-in (in-bound):* Messaging will include a prompt to agree to scheduling, which will be following by a prompt to call the Penn Medicine COVID-19 Vaccine Scheduling Hotline.

Among Arms 2-3, patients will be additionally randomized to different messaging content informed by principles of behavioral science in a 1:1:1:1 ratio (2,500 in each arm):

- *Arm A: Standard messaging:* The message describes that the patient is eligible for the COVID vaccine. ("Our records show you are eligible for your COVID-19 vaccine at Penn Medicine.")
- *Arm B: Clinician endorsement:* The message will describe an endorsement from the provider to get the vaccination. ("[name] recommends that you receive the vaccination.")
- *Arm C: Scarcity:* The message will highlight the limited availability and the elevated priority for the patient to receive the vaccine at Penn Medicine. ("You have been selected to receive from the limited supply of COVID-19 vaccine at Penn Medicine.")
- *Arm D: Opt-out framing:* This will highlight that a vaccine is reserved for the patient, implying that they need to opt-out ("We have reserved a COVID-19 vaccine appointment for you at Penn Medicine.").

All study arms will be further randomized into 5 smaller batches of 500 patients each (100 in the phone

call only arm). All patients assigned to batch 1 will receive messages on the same day, per their study arm assignment. A total of 4,000 initial outreach text messages and 100 phone calls will be sent each day for 5 days until all 20,500 patients have been contacted. Batched messaging will help evenly spread the call volume for the Access Center and help balance scheduling capacity with vaccine supply.

Text Messaging:

All eligible patients randomized to the text message arms will receive text messaging about the COVID vaccine from Penn Medicine. The first message will describe that it is from Penn Medicine, ask the patient to confirm their name, and allow for patients to opt-out of further outreach. If the patient confirms, the 2nd text message will describe that patients are eligible for the COVID 19 vaccine (“Our records show you are eligible for your COVID-19 vaccine at Penn Medicine.”). This will be followed by a behaviorally-informed messaging prompt (“YES”), followed by the mechanism through which the patient can get scheduled for the vaccine. At the end of the message, there will also be a prompt for more information (“INFO”), to defer the vaccine for now (“NOT NOW”), or to indicate vaccination has already been completed (“DONE”).

If no reply is received and the patient has not opted out of messaging or deferred the vaccine (“NOT NOW”), they will receive up to 2 reminder texts 2 and 4 days after initial outreach.

Arms 2 will require patients to opt-in to receive a call back from Access Center representatives. Arm 3 will require patients to opt-in to receive the vaccine scheduling hotline number and call to schedule themselves. This information will be captured in the Way to Health platform and will be securely transmitted in a report to the Access Center daily.

Questions that are submitted by patients via text will be manually reviewed and responded to or routed as appropriate.

Analysis Plan

The primary outcome will be the percentage of patients who complete the first dose of the COVID vaccine within 1 month of initial outreach. Secondary outcomes will be the completion of the first dose within 2 months, and completion of the vaccination process within 2 months of initial outreach. Additional outcomes will include the percentage of patients with invalid cell phone numbers (either wrong or non-textable numbers), non-response to text messaging, the percentage of patients that are scheduled, text message responses (YES, INFO, NOT NOW, DONE), and number of phone calls made by the access center. Heterogeneity of subgroup response through interaction analysis will be examined controlling for patient portal/email status, age, race/ethnicity, sex, insurance, and income (by zip code). We will also examine vaccine completion by vaccine type, and code and examine non-keyword replies for themes.

We estimate a 5% response rate to the phone call only. In order to minimize the outgoing phone call burden on the access center, we will include 500 patients in the outbound phone call arm (Arm 1). For the scheduling flow comparison, we will allocate 10,000 patients in each text message arm (Arms 2-3). We will compare each text message arm to the phone call arm, resulting in 2 comparisons (arm 2 vs arm 1, arm 3 vs arm 1). Accounting for 2 pairwise comparisons with a P-value threshold of .025 (Bonferroni correction; .05/2), we estimate over 85% power to detect a difference of 4 percentage points (response

rate of 9%) using the chi-squared test of proportions [STATA: power twoprop .05 .09, n1(500) n2(10000) a(.025)].

For the messaging comparison, we will allocate 2,500 patients in each arm. We will compare arms B-D to Arm A with 3 pairwise comparisons. Assuming a P-value threshold of .017 (.05/3) and a baseline response rate of 8% for text messaging, we estimate approximately 87% power to detect a difference of 2 percentage points (response rate of 10% for intervention arms) using the chi-squared test of proportions. [STATA: power twoprop .08 .10, n1(5000) n2 (5000) a(.017)]. We do not anticipate interaction between scheduling workflow and messaging arms.

Subject Confidentiality

Information about study subjects will be kept confidential and managed according to the requirements of the Health Insurance Portability and Accountability Act of 1996 (HIPAA). All PHI will be maintained on UPHS servers. Source documents are maintained in PennChart. No source documents will be printed or maintained in paper form at the study site. Data from PennChart will be recorded in Penn Medicine's REDCap system. The investigator and study team will have access to PHI within PennChart and REDCap. We will label all PHI within REDCap as identifiable information so that de-identified exports are possible. All reports that include identifiable information will be stored on the Innovation Center secure drive, maintained behind the UPHS firewall. Direct identifiers will be maintained on RedCap until manuscript publication in case additional chart review is needed for confirmation of results. Once data analysis and manuscripts have been published, direct identifiers will be deleted from RedCap and the de-identified database will be stored on the Innovation Center secure drive.

Sensitive Research Information

This Research does not involve collection of sensitive information about the subjects that should be excluded from the electronic medical record.

Subject Privacy

20,500 patients will be identified through automated data extraction from the electronic health record (EHR). The research team will have no direct interaction with study participants. Text messaging will be conducted via the Way to Health platform. The initial text message will confirm identity prior to proceeding with additional text messaging for the intervention.

Data Disclosure

Patients in Arm 2 who agree to scheduling an appointment for COVID-19 vaccination will receive up to 3 phone calls from Penn Medicine Access Center representatives in an attempt to schedule them for their appointment. As such, patients will be identified in EPIC via a scheduling queue for Access Center representative call queue purposes.

Consent

1. Consent Process

Overview

Waiver of consent for this study is requested. Please see below.

Children and Adolescents

Not applicable.

Adult Subjects Not Competent to Give Consent

Waiver of consent is being requested.

2. Waiver of Consent

Waiver or Alteration of Informed Consent*

Waiver or alteration of required elements of consent.

Minimal Risk*

This study involves no more than minimal risk to subjects. Outreach for COVID-19 vaccination is an operational imperative and this trial is embedded in routine clinical operations at Penn Medicine. All participants will receive messaging indicating they are eligible to receive the vaccine as well as a prompt for scheduling. The only research related activity is the randomization of patients to different types of scheduling and messaging strategies that will help inform best practices for future outreach to other patient populations. Participants must still consent to receive the vaccine at the time of vaccination, as is usual care.

Impact on Subject Rights and Welfare*

Subjects rights and welfare will not be adversely affected by the waiver of authorization and consent. All subjects will have the opportunity to voluntarily receive or not receive the COVID-19 vaccination. This trial aims to identify outreach approaches that might increase uptake.

Waiver Essential to Research*

We believe that we would not be able to practically conduct the research without waiver of consent. If we had to obtain either written or verbal consent ahead of time, it would substantially limit our study population and it may alter their participation in the intervention. Thus, we would only learn about the response rate for patients who we were able to speak to for consent. This would limit the generalizability to practice. We believe that subsequent completion of vaccination or deferral of participation in vaccination is still completely voluntary, and participants must provide consent at the time of vaccination. Obtaining waiver of consent would allow us to avoid the potential selection/volunteer bias for inclusion of patients particularly interested in vaccination that can occur when consent is required. Since our main objective is to understand the potential influence varying outreach strategies on participant behavior, we believe that obtaining consent would not be practicable. Additionally, we have received waiver of consent for similar studies related to population health outreach in the past.

Additional Information to Subjects

Participants who are vaccinated will be provided with appropriate information about possible side-

effects and follow-up as per current vaccine guidelines and Penn Medicine standards of care. Participants will be offered their 2nd dose appointment as appropriate per the type of vaccine given at the first appointment.

Written Statement of Research*

We do not believe it would be reasonable to inform patients of their participation in this behavioral outreach study upon completion, as conveying the intent of the research (that it is not a vaccine trial) to a lay population would likely lead to unnecessary confusion. Calling all patients would be infeasible, and sending a text message would not be a sufficient platform to explain the nuances of the study. Text messaging might also crowd out other more important messaging from Penn Medicine about health promotion. As this is a behavior observation study and all participants will receive outreach, we feel the risk of harm from informing participants is greater than not informing them.

Risk / Benefit

Potential Study Risks

The risks associated with this study are no more than minimal. There is the potential risk of breach of confidentiality. We will minimize this risk by using de-identified information whenever possible and by maintaining all identifiable information on a secure drive and/or in a HIPAA-compliant system (e.g. REDCap) as is already being done through routine clinical operations. There is also the risk of physical discomfort from the vaccine. We will minimize this risk by communicating the potential discomforts at the time of the vaccination and by offering routine monitoring, as is the current standard practice for COVID-19 vaccinated patients at Penn Medicine.

Potential Study Benefits

If a participant completes their COVID-19 vaccination, they will potentially benefit by dramatically reducing the likelihood of infection by COVID-19 causing severe complications, hospitalization or death. Additionally, their vaccination will potentially benefit the population by increasing the overall rate of immunity and slowing disease spread among those unable to receive the vaccine. Information learned from this study may additionally benefit society through a better understanding of how to effectively increase overall uptake of the COVID-19 vaccination, which could inform future vaccination campaigns or be applied to other population-wide contexts.

Alternatives to Participation (optional)

Participants may choose to opt-out of receiving text messaging and/or decline scheduling their vaccination.

Data and Safety Monitoring

Safety will be overseen by the PI and the study team. In the case of possible events, the PI or designee will review the study charts to evaluate events at each subject interaction to ensure the grade, relationship to the study procedure, expectedness, and the course of action for each subject is documented.

Risk / Benefit Assessment

The risks associated with this study are no more than minimal. Better knowledge of how to increase

COVID-19 vaccine uptake could potentially address a major source of disparities among our patient population. Better vaccine uptake could potentially reduce the already increased disease burden on our most at-risk patients. For these reasons and those outlined in the above benefits section, the investigator believes that the risks of participating in the study are outweighed by the potential benefits of participating in the study.

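### Should the plan have compared the four messages among patients who confirmed their identity, as well as among all randomised?

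*Combined protocol and SAP*

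**What the plan says.** Under Procedures, Text Messaging, the first text identifies the sender, asks the patient to confirm their name and offers a way out of further messages. The next step is conditional: "If the patient confirms, the 2nd text message will describe that patients are eligible for the COVID 19 vaccine". The arm content comes after that: "This will be followed by a behaviorally-informed messaging prompt". Subject Privacy repeats the order: "The initial text message will confirm identity prior to proceeding with additional text messaging for the intervention". The first text is described once for all text arms, with no arm-specific wording. For patients who do not reply, "they will receive up to 2 reminder texts 2 and 4 days after initial outreach"; what those reminders contain is not described.

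The Analysis Plan defines the primary outcome as the percentage of patients with a first dose in the month after outreach begins. For the messages, "We will compare arms B-D to Arm A with 3 pairwise comparisons". On an 8% baseline, with a threshold of .017 and 5,000 per arm in the Stata call, "we estimate approximately 87% power to detect a difference of 2 percentage points". Invalid numbers, non-response, scheduling and the keyword replies are further outcomes. No analysis restricted to confirmers is specified.

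**The concern.** Aim 3 is "To compare the equity and efficiency of different messages informed by behavioral science, including PCP endorsement, opt-out framing, and scarcity". If the wording reaches only those who pass the name check, every arm contains patients on whom it cannot act, and comparing all of them dilutes the contrast. The most serious consequence would be a power error. Suppose the 2-point gain were expected only in patients who saw the message, and half did. The difference between arms would then be 1 point, and power at 8% v 9% with 5,000 per arm would be 27.6%, not 87%.

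Short of that, there seems to be a missed opportunity. The name check appears to be common to A to D, so who confirms cannot depend on the message. Confirmers could then be compared without breaking the randomisation, which is not true of an ordinary per-protocol subset. If such an analysis is not prespecified, it can later be read only as post hoc.

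**Working it through.** **1. The plan's own figure.** Inputs from the Analysis Plan: 8% v 10%, 5,000 per arm, two-sided threshold .017 (critical value 2.387).

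- Null SE = √(2 × .09 × .91 / 5000) = .00572
- Alternative SE = √[(.08 × .92 + .10 × .90) / 5000] = √(.1636 / 5000) = .00572
- Power = Φ[(.02 − 2.387 × .00572) / .00572] = Φ(1.11) ≈ 86.6%

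This matches the stated 87%. The two rates apply to 5,000 allocated patients per arm, so they already include patients who never reply. The 27.6% case does not arise from the plan's inputs. The 95% half-width for the difference is 1.96 × .572 = 1.12 points.

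**2. What a confirmer comparison could add.** Let c be the confirming share and b the first-dose uptake in non-confirmers. Neither is in the documents; c = 25% to 90% and b = 0 to 5% are assumed. Keep 8% v 10% overall and place the whole effect in confirmers:

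- control rate in confirmers = [.08 − (1 − c)b] / c
- difference in confirmers = .02 / c
- patients per arm = 5000c

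Multiplying the confirmer difference by c, treated as known, returns it to the all-randomised scale. Worked case, c = 50%, b = 0: 16% v 20% in 2,500 per arm. SE = √[(.16 × .84 + .20 × .80) / 2500] = .01085; times .5 = .00543; half-width 1.06 points.

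| c | Half-width, b = 0 | Half-width, b = 5% | Power at .017, b = 0 | Power at .017, b = 5% |
|---|---|---|---|---|
| All randomised | 1.12 | 1.12 | 86.6% | 86.6% |
| 90% | 1.11 | 1.09 | 87.0% | 88.8% |
| 75% | 1.10 | 1.03 | 87.9% | 92.0% |
| 50% | 1.06 | 0.93 | 90.3% | 96.6% |
| 25% | 0.94 | 0.79 | 96.3% | 99.4% |

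The direction is guaranteed when the message does nothing in non-confirmers. With overall rate p and confirmer rate q, p(1 − p) − cq(1 − q) = (1 − c)b(1 − b) + c(1 − c)(q − b)², which is never negative. The size is not guaranteed. The c = 25% row needs an 8-point effect among confirmers (.02 / .25). The b = 5% columns assume that patients who saw no arm wording take up vaccine at the same 5% the plan expects from the phone-call arm.

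**3. What would change.** A supportive analysis would carry no alpha, so the power columns describe a test that nobody would use to decide Aim 3. Only the interval widths are relevant, and the decisive comparison keeps its 86.6%.

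**4. Which question is asked.** The Background section wants the outreach approach with the highest response rate, and Study Design calls the trial pragmatic. The outcome is a percentage of patients from initial outreach. For a health system choosing a message to send to everyone, the all-randomised difference is the target, non-repliers included.

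**5. Whether the confirmer effect is lost.** If the message has no effect in non-confirmers, the effect in confirmers is the planned difference divided by c, for example 2 / .5 = 4 points. Only some precision is forgone. Replies to the keyword prompts, which come in the text sent after confirmation, are also planned outcomes and say something about patients who were reached.

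**The case for a change.** The strongest opposing case is that the extra analysis is nearly free. The platform must record the confirmation reply in order to send the second text. A common name check makes the confirmer comparison a properly randomised one, and its rescaled estimate cannot be less precise when non-confirmers are unaffected. One sentence before unblinding of results would protect it from being read as post hoc. All of that is correct, and an investigator who wanted to add it would do no harm.

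Two gaps in the text are also real. Reminder content is not described, and the Minimal Risk paragraph of the consent waiver says that all participants get an eligibility message and a scheduling prompt, which does not fit text-arm patients who never confirm. Similarly, "All eligible patients randomized to the text message arms will receive text messaging about the COVID vaccine from Penn Medicine" reads as unconditional until the sentences after it set the condition. The waiver paragraph is a general statement that also covers the phone arm, not a delivery specification.

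These gaps favour the planned analysis. If reminders carried arm wording to patients who had not confirmed, the message could influence who confirms and could act on non-confirmers. The confirmer comparison would then lose its randomised footing and its precision guarantee, while the all-randomised comparison would stay valid. It is also fair to note that the plan does not define non-response as non-confirmation, so the confirming share may be known only approximately from the listed outcomes.

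**Conclusion.** The concern does not hold. The comparison of B, C and D with A in all randomised patients is unbiased, answers the pragmatic question and has the power claimed for it (86.6% against a stated 87%). That figure rests on 5,000 per message arm, pooled over the two text workflows as in the Stata call. Leaving out a confirmer analysis costs the primary conclusion nothing. What is forgone is some precision on a supportive estimate: a 95% half-width of 1.11 to 0.79 points instead of 1.12 over the assumed range, and no lower than 1.06 if at least half confirm and non-confirmers are not vaccinated. Even that depends on a confirming share and a non-confirmer uptake absent from the documents, and on reminders that carried no arm wording to non-confirmers. The unstated reminder content and the loosely worded waiver paragraph are matters of missing detail and do not affect the planned result.

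### Do the text-versus-phone comparisons go wrong because each text arm averages over four message wordings?

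*Combined protocol and SAP*

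**What the plan says.** The Objectives keep two questions apart: Aim 2 concerns scheduling workflows and Aim 3 concerns message content. Study Design describes a factorial trial with 500 patients in the phone arm and 10,000 in each of two text arms. Within the text arms, four messages are allocated equally. The Randomization section gives the cell size as "in a 1:1:1:1 ratio (2,500 in each arm". This reads as the number per workflow, since Study Design gives 5,000 per message over both workflows. Of the phone arm the same section says: "Patients randomized to this arm will not receive any text messaging".

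The Analysis Plan then treats the two factors in turn.

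- **Workflow:** "For the scheduling flow comparison, we will allocate 10,000 patients in each text message arm". The tests follow as "We will compare each text message arm to the phone call arm". That makes two tests, Arm 2 against Arm 1 and Arm 3 against Arm 1, each at a threshold of .025.
- **Messages:** "We will compare arms B-D to Arm A with 3 pairwise comparisons", each at .017, assuming "a baseline response rate of 8% for text messaging" and 10% for a better message.
- **Both factors:** "We do not anticipate interaction between scheduling workflow and messaging arms".

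The chi-squared test is named for both sets. No effect estimate or confidence interval is named for any comparison.

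**The concern.** The label given to the workflow comparison suggests that it isolates scheduling. It does not isolate scheduling from wording, because the phone arm has no wording level against which the text wordings could cancel. The statement that no interaction is expected does not help. It concerns workflow by message within the text arms, and even purely additive wording effects stay in a text-versus-phone difference.

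A health system that would send only the plain message would want standard text against phone, with its uncertainty. If it read the whole-arm difference as that quantity, it would be off by the average wording effect, and the interval would be centred on the wrong value. The plan lists no comparison that gives the standard-text figure directly.

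**Working it through.** **Inputs.** From the Analysis Plan: phone 5%, text arm 9% for the workflow power, standard text 8%, better message 10%, thresholds .025 and .017. From Study Design and Randomization: 500 phone patients, 10,000 per text arm, 2,500 per workflow-by-message cell. Taking 8% as the Arm A rate in both workflows is an assumption.

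**1. The plan's own figure.** Two-sided chi-squared test with pooled variance under the null, 500 v 10,000:

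- pooled rate = (25 + 900)/10,500 = 0.0881
- null SE = √(0.0881 × 0.9119 × (1/500 + 1/10,000)) = 0.01299
- alternative SE = √(0.05 × 0.95/500 + 0.09 × 0.91/10,000) = 0.01016
- power = Φ((0.04 − 2.241 × 0.01299)/0.01016) = Φ(1.07) = 0.858

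This matches the stated figure of over 85%. The message comparison (5,000 v 5,000, 8% v 10%, .017) gives 0.866, against the stated 87%. That calculation pools each message over both workflows, just as the workflow comparison pools over messages.

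**2. What the workflow comparison estimates.** With additive effects and b the difference of a message from Arm A:

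whole-arm difference = (standard text − phone) + (b_B + b_C + b_D)/4.

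This is the effect of the text programme with its four messages in equal shares. Randomisation protects it whether or not the messages differ.

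**3. Whether mixing messages upsets the test.** With two messages at 8% and two at 10%, the average within-message variance is (2 × 0.0736 + 2 × 0.0900)/4 = 0.0818. The chi-squared test uses 0.09 × 0.91 = 0.0819. The difference is negligible and on the conservative side.

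**4. How far apart the two quantities are.** Let k of messages B to D be 2 points above A. The averages are (8(4 − k) + 10k)/4.

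| k | Text-arm average | Whole-arm difference | Standard text v phone | Gap | Power, whole arm |
|---|---|---|---|---|---|
| 0 | 8.0% | 3.0 | 3.0 | 0 | 0.59 |
| 1 | 8.5% | 3.5 | 3.0 | 0.5 | 0.74 |
| 2 | 9.0% | 4.0 | 3.0 | 1.0 | 0.86 |
| 3 | 9.5% | 4.5 | 3.0 | 1.5 | 0.93 |

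Differences and gaps are in percentage points. The whole-arm 95% half-width at 9% v 5% is 1.96 × 0.01016 = 1.99 points, so the gap is below sampling error in every row.

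**5. What misreading would cost.** If the whole-arm 95% interval is taken as an interval for standard text v phone, it covers the 3-point difference in about 94, 89, 79 and 65% of simulated trials for k = 0 to 3. These figures do not measure an error in the planned interval or test. An interval aimed at 4.5 points should often miss 3 points. Milder patterns give less: one message at +1 point gives 92.5%, messages at +2, −1 and 0 give 92.5%, and all three at +1 give 85%.

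**6. Whether the standard-text figure is lost.** It is not. Under no interaction it equals the whole-arm difference minus one quarter of the sum of the three planned message differences. In units of the outcome variance, the standard-text mean then has variance 1/10,000 + (1/5,000 − 1/20,000) = 1/4,000. At 8% v 5% the 95% half-width is 1.96 × √(0.0000950 + 0.0736/4,000) = 2.09 points. Arm A alone gives 1.96 × √(0.0000950 + 0.0736/2,500) = 2.19. As a test at .025 it would have power of only 0.56 or 0.54.

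**The case for a change.** The best case for acting has three parts. First, the plan's figures hint at the issue: a 9% text arm and an 8% standard message fit together if, say, two of the three other messages add 2 points, so 1 of the 4 powered points would be wording. Second, the Background wants results that other health systems can use, and some may be able to send only plain texts. Third, the extra estimate costs one model and no patients or alpha.

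The arithmetic in this stands, and so does the point about reading: a report should describe these results as text outreach averaged over the messages sent. The rest does not make a fault. The 8% and 9% do not conflict; the 9% is the alternative for a whole arm, and the 8% is the baseline for the message comparison. Where messages do not differ, the whole-arm result is already the standard-text result. Where one clearly helps, there is less reason to send only the plain one. The extra estimate would not isolate scheduling either, because channel, name check and reminder texts would still differ from phone.

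The absence of a named confidence interval applies to every comparison in the plan, so it is not a defect of this one. Arm 2 against Arm 3 does balance wording, but whether to report it is a separate matter.

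**Conclusion.** The concern does not hold. Followed as written, the plan gives two valid randomised comparisons of a text programme with phone, each with the power that the plan states. Averaging one factor over the levels of another is the ordinary marginal comparison in a factorial design. The average wording effect is part of what the comparison is meant to measure, and the plan never calls it standard text against phone.

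The gap between the two quantities is 0 to 1.5 points if phone is 5%, standard text is 8%, wording effects are additive and each other message adds 0 or 2 points. It would be smaller if effects were smaller or of mixed sign. A supporting estimate of standard text against phone would be reasonable, but leaving it out makes no planned result wrong.
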